### Exclusion criteria

- Initiation or discontinuation of a medication known to affect body weight or insulin sensitivity within 3 months of enrollment (e.g. hormonal contraception, psychiatric medications: tricyclic antidepressants, monoamine oxidase inhibitors, paroxetine, escitalopram, lithium, olanzapine, clozapin, risperidone, carbamazepine, valproate, divalproex, mirtazapine)
- Use of weight-loss medications or diabetic medications in the preceding 1 year (e.g. metformin, sulfonyleureas, insulin, etc)
- Antibiotic use in the preceding 6 months
- Delayed gastric emptying syndrome
- Known chronic aspiration
- Swallowing dysfunction or oral-motor dyscoordination, or inability or unwillingness to swallow multiple large capsules
- Malabsorptive disorders including celiac disease, cystic fibrosis, irritable bowel syndrome, prior gastrectomy, bariatric surgery and any state of chronic diarrhea
- Pregnant women or women trying to conceive or women who are breastfeeding; women of child-bearing potential will have a urine or serum hCG test.
- Patients with an acute illness or an acute exacerbation of underlying co-morbid condition
- Subjects on high dose steroids ( $>40$  mg daily)
- Subjects on multiple/combination immunosuppressive regimens including high dose corticosteroids, calcineurin inhibitors, mTOR inhibitors, lymphocyte depleting biologic agents, anti-TNF agents.
- Patients with a history of HIV, hepatitis B, hepatitis C, decompensated cirrhosis, recent bone marrow transplant, other causes of severe immunodeficiency.
- Patients with a history of significant allergy to foods not excluded from the donor diet (excluded foods are tree nuts, peanuts, shellfish, eggs)
- Allergy to chocolate/cocoa or gelatin, or unwillingness to ingest gelatin (in placebo capsules).
- Screening labs: AST or ALT  $>3x$  normal; Hematocrit  $<33\%$ ; White Blood Cell count  $<3000$  cells/uL; ANC $<500$ ; Creatinine  $>2.0$  mg/dL
- Patients with abnormal bowel habits, e.g. constipation with  $<4$  bowel movements/week

## **IV. SUBJECT ENROLLMENT**

### Methods of enrollment:

Obese adults will be recruited from the MGH Weight Center. The PI does not perform clinical work at the MGH Weight Center. However, if a patient of the PI's is identified who may be eligible for the study, the PI will ask a physician colleague to explain the study and will provide patients the Consent Form to review at home. In addition, recruiting advertisements will be posted on email, the internet, and by flyer. Finally, we will add the study to the <https://register.clinicaltrials.gov> database. All letters and advertisements will be approved by the Partners IRB before they are used. All eligible obese subjects will be invited to participate in the hyperinsulinemic-euglycemic clamp substudy.

### Optional Substudies

All participants will be asked if they are interested in participating in the optional substudies as part of the initial screening process. The first substudy is to examine associations of gut microbiome with bone density (Aim 3). The second substudy is an extension the main study's stool and blood sampling to determine the longevity of any effects observed as a result of FMT. If participants express interest, they will be enrolled in the substudies.

### Informed consent

Written informed consent will be obtained by a nurse practitioner or physician investigator. In situations where a nurse practitioner is obtaining consent, subjects will be offered the option for further discussion with a physician investigator if they have any remaining questions. This offer will be documented in the research record. Any consent problems will be reported to the PHRC in real-time.

### Randomization

Obese recipients will be randomized to receive either FMT or placebo capsules in a 1:1 ratio. Double blinding is important. Subjects will be assigned by a computer generated randomization order known to an individual not involved in assessing the patients. This individual will identify the assignment, take appropriate capsules from relevant freezer locations, and place them on dry ice as usual for administration, but place them in a vial labelled "STUDY Caps" for administration so neither physician nor subject will be able to identify real vs placebo capsules. The actual labeled containers identifying caps as real or placebo will then be sealed in an opaque envelope and saved for review at the time of unblinding. This will serve as a "double check" on actual assignment.

## **V. STUDY PROCEDURES**

Lean donors will undergo testing and follow procedures outlined in protocol 2014P002706. Main procedures will occur in the primary 12-week study period; a supplemental week 24 phone-call will be performed for a safety check. In addition, samples of the fecal collection will be stored at -80°C for further microbiome analysis.

Obese recipients will undergo the following procedures:

Phone Screen (10-20 minutes)

Screen Visit (30 minutes)

- Review eligibility and understand/see size of capsules
- Obtain informed consent
- Height, weight measurements to determine eligibility
- Screening labs: Complete blood cell count w/ differential, comprehensive metabolic panel, HIV Ab, HBV sAb/sAg, HCV Ab, fasting insulin and glucose.
- Subjects will be counseled not to start any new major dietary changes, exercise regimens, or medications throughout the primary 12-week study period
- Subjects will be given information about how to perform fecal collections (see Stool Collection document)

Baseline Visit, Week 0 (Day 1: 5 hours, Day 2: 15 minutes, Day 3: 15 minutes)

- Fasting blood samples for measurements of HOMA-IR, lipids, CRP, and HbA1c.
- Women of child bearing potential will have a urine pregnancy test
- Height, weight measurements
- 48-hour food recall
- Whole body DXA scan for body composition analysis
- DXA scan of lumbar spine and hip to assess baseline BMD (optional substudy)
- Fecal collection
- Indirect Calorimetry
- Hyperinsulinemic euglycemic clamp
- After above study procedures are complete, subjects will receive FMT (or placebo) caps, 15 capsules on each of 2 successive days. Note that participants will need to either fast for 4 hours after the clamp or return on the subsequent day for their first capsule administration.

Weeks 1-5 (15 minutes)

- Interval side effect assessment (see Side Effect Assessment document)
- Subjects return for weekly administration of 15 capsules (for a total of 6 weeks, including Week 0)
- Fecal collection at weeks 1, 3 and 5.

Week 6 (5 hours)

- Interval side effect assessment (see Side Effect Assessment document)
- Height, weight measurements
- Women of child bearing potential will have a urine pregnancy test

- Fasting blood samples for measurements of HOMA-IR, lipids, CRP, and HbA1c.
- 48-hour food recall
- Fecal collection
- Whole body DXA scan for body composition analysis
- Fecal collection
- Indirect Calorimetry
- Hyperinsulinemic euglycemic clamp
- Note that we will allow a +1 week window for scheduling the week 6 visit

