FMT and placebo capsule administration: Subjects will be NPO at least 4 h prior to and for 1 hour following capsule intake on each day, to minimize risk of vomiting during ingestion of capsules. Subjects will be handed each capsule by an investigator and asked to take each capsule with a sip of water. Subjects will be asked to drink at least 12 oz of water during administration to facilitate dilution of stomach contents and transit into the small intestine. In the event of vomiting subjects will be observed, and not re-dosed.

Subjects are evaluated after taking capsules by the study investigators, typically for 15 minutes. Immediate side effects are very uncommon in our experience. Capsules are odorless and tasteless and do not dissolve in the acidic environment of the stomach. (In our study of capsules to date we have had 1/61 subjects who complained of nausea during administration, and this individual had concurrent psychiatric illness and concurrent irritable bowel syndrome diagnosed by an outside gastroenterologist. One child vomited 4 hours after capsules were administered.).

Subjects receive a copy of the signed consent form to take home and an information sheet (attached) on symptoms to monitor and study physician phone numbers. All patients have our contact numbers and will be encouraged to call for any concerns. Subjects are asked to inform us if they require the initiation of antibiotics for intercurrent clinical illness, during the study period.

Subjects will receive capsules at weekly intervals ( $\pm$  2 days) for weeks 0-5.

Subject counseling: Subjects will be counseled to remain on the same diet that they are currently on and not to initiate any major exercise regimens throughout the primary 12 week study period. In addition, women with child-bearing potential will be informed that they need to use contraception throughout the study. If they are taking a hormonal contraceptive, they need to remain on such until the end of the study. If they are not using a hormonal contraceptive, they will need to use other forms of birth control, such as barrier methods with a spermicide, IUD, or abstinence. We will ask that they not actively initiate or discontinue hormonal treatments during the study, as this may confound our assessments of body weight and insulin sensitivity.

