#### **D. Safety Monitoring**

Obese recipients will be monitored for clinical safety by history (and standard exams when seen in person) by asking open ended and then directed questions. Subjects will be followed closely, as noted above. Follow up calls made by a study coordinator will be documented and follow up information is reviewed on the same day with a study physician if any symptoms of concern are identified. A physician plan for ongoing follow-up will be noted and implemented. In any case of adverse events identified as grade 2 (moderate severity) an in-person visit with an investigator, either in the GI or ID outpatient practices, will be encouraged.

An AE will be considered related if, in the judgment of the treating physician it is both temporally related to administration of the capsules, and there is no other reasonable alternative explanation, and the AE is not more reasonably attributed to progression of the underlying illnesses.

Any serious adverse event (SAE) assessed as possibly, probably, or definitively related to fecal transplantation will be reported in an expedited fashion to the IRB and FDA. SAE's are defined as any Grade 3 or 4 events as described on the attached AE grading chart, in addition to any event temporally associated with the study procedure that:

- results in death;
- is life threatening (places the subject at immediate risk of death from the event as it occurred);

- requires inpatient hospitalization or prolongation of existing hospitalization;
- results in a persistent or significant disability/incapacity;
- results in a congenital anomaly/birth defect;
- any other adverse event that, based upon appropriate medical judgment, may jeopardize the subject's health and may require medical or surgical intervention to prevent one of the outcomes listed above.

Investigator monitoring with IRB and FDA oversight/reporting is proposed.

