## **VI. BIostatistical Analysis**

Change in insulin sensitivity is the primary outcome and will be compared between placebo and FMT groups over 12 weeks using longitudinal regression models. Secondary outcomes including change in insulin sensitivity, lipids, CRP, and DXA body composition will be similarly investigated. This is a pilot study to determine feasibility

and safety, and to obtain data for power calculations for a larger powered study. After accounting for 15% dropout rate, and assuming a standard deviation of insulin sensitivity of 30-45% and a two-sided alpha of 0.05, this pilot study (n=12 per group) has 80% power to detect a 40-60% difference in insulin sensitivity between groups, and a 30-45% difference from baseline within each group. After accounting for 15% dropout rate, and assuming a standard deviation of weight loss of 5% and a two-sided alpha of 0.05, this pilot study (n=12 per group) has 80% power to detect a 6.6% difference in weight loss between groups, and a 5% difference in weight loss from baseline within each group.

Fecal samples from lean donors and obese recipients will be stored, as noted above. If funding allows in the future, these samples will undergo microbial analysis using 16S ribosomal DNA-based identification and deep sequencing techniques. Changes in the composition of the gut microbiota and metagenomic pathways will be correlated with clinical changes in metabolism.

Bone mineral density (BMD) of the spine, hip, and whole body will be assessed at baseline and at 12 months. This pilot study will provide preliminary data to explore the associations between BMD and gut microbiota prior to manipulation and after FMT.

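### No symptom assessment is scheduled before the first capsules at week 0, so there is no per-participant baseline against which to judge new or worsened side effects.

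*Combined protocol and SAP*

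**What the plan says.** Section V (Study Procedures) sets out the content of each visit. The Screen Visit covers eligibility ("Review eligibility and understand/see size of capsules"), consent, height and weight, laboratory tests, counselling and stool-collection information. The Week 0 list covers fasting bloods, a pregnancy test, height and weight, food recall, DXA, stool, calorimetry and the clamp. Dosing then follows: "After above study procedures are complete, subjects will receive FMT (or placebo) caps, 15 capsules on each of 2 successive days". Neither list has a symptom or side-effect item.

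The first such item is under Weeks 1-5: "Interval side effect assessment (see Side Effect Assessment document"). It is repeated at weeks 6 and 12, at week 24 (by phone, or in person for extension participants) and at month 12.

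Two other places bear on the point. Section V.C describes observation around dosing, but only afterwards: "Subjects are evaluated after taking capsules by the study investigators, typically for 15 minutes". Section V.D describes how safety history is taken, "Obese recipients will be monitored for clinical safety by history (and standard exams when seen in person) by asking open ended and then directed questions", without naming a time point before the first dose. Section V.D also requires, for an event to count as related, that "in the judgment of the treating physician it is both temporally related to administration of the capsules, and there is no other reasonable alternative explanation".

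On the role of safety, section VI says "This is a pilot study to determine feasibility" and names safety alongside it. Aim 2 in section II makes FMT-related adverse events a secondary outcome.

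**The concern.** The metabolic and body-composition measures scheduled at follow-up (HOMA-IR, clamp, lipids, CRP, HbA1c, weight, DXA, calorimetry) each have a value from before the first capsule. Symptoms do not. Directed questions asked a week after dosing will pick up some complaints that were there already, such as occasional bloating, reflux or loose stools, and the schedule requires no earlier record to set them against.

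Two uses of the safety data are exposed. The first is the relatedness judgment, which is made event by event. It turns on timing and on whether "there is no other reasonable alternative explanation, and the AE is not more reasonably attributed to progression of the underlying illnesses". Both questions ask what was present before dosing. The second is the event rate within each arm, which a pilot passes on to the planning of a larger study. Background symptoms counted as new would raise that rate in both arms. In arms of 12, one participant is 1/12 = 8.3 percentage points, so a few misclassified reports change the safety summary visibly.

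**Working it through.** **Step 1. Schedule check (section V).**

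| Visit | Capsules given | Side-effect item listed |
|---|---|---|
| Screen | no | no |
| Week 0 | yes, on two days | no |
| Weeks 1-5 | yes, weekly | yes |
| Week 6 | no | yes |
| Week 12 | no | yes |
| Week 24 | no | yes |
| Month 12 (extension) | no | yes |

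The first scheduled assessment comes about a week after the first capsules. Sections V.C and V.D add no assessment before the first dose.

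**Step 2. What eligibility removes (section III, Exclusion criteria).** The criteria exclude irritable bowel syndrome, malabsorptive disorders, chronic diarrhoea, delayed gastric emptying, swallowing dysfunction, acute illness or acute exacerbation of a co-morbidity, and abnormal bowel habits, the last with constipation given only as an example. Mild or intermittent symptoms can still pass. Eligibility is also a yes/no decision and leaves no graded value against which worsening can be measured.

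**Step 3. Chance imbalance between the arms.** The plan gives no figure to reproduce here, so this is an illustration.

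- Arm size: n = 12 FMT and 12 placebo (section III).
- Proportion p with a mild prior symptom: not in the documents; assumed 10% to 40%.
- Model: the numbers with a prior symptom, X and Y, are independent Binomial(12, p).
- Formula: P(|X − Y| ≥ k) = Σ b(i) b(j) over all i, j with |i − j| ≥ k, where b(i) = C(12, i) pⁱ (1 − p)¹²⁻ⁱ.

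| p | Expected per arm (12p) | P(differ by ≥ 2) | P(differ by ≥ 3) | P(differ by ≥ 4) |
|---|---|---|---|---|
| 10% | 1.2 | 0.289 | 0.084 | 0.018 |
| 20% | 2.4 | 0.438 | 0.197 | 0.071 |
| 30% | 3.6 | 0.503 | 0.263 | 0.116 |
| 40% | 4.8 | 0.532 | 0.297 | 0.143 |

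A gap of 3 people is 3/12 = 25 percentage points. Its probability (3 or more, either direction) is about 8% to 30%. Half of that, about 4% to 15%, is the chance that the excess falls in the FMT arm.

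**Step 4. How to read the table.** These are probabilities of imbalance in prior symptoms. They become imbalances in recorded events only if each prior symptom is reported after dosing and counted as new, so they are upper-end illustrations. A gap of 2 people is weak evidence of anything in arms this small: two-sided Fisher p = 0.48 for 2 v 0 and 0.59 for 3 v 1. That is why the 3-or-more column is used for the size of the problem.

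**The case against.** The strongest reply is that the plan already handles most of this.

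- **Randomised, blinded placebo arm.** Background symptoms are elicited equally in both arms, so the between-arm comparison is unbiased on average. This stands. It does not show which individual events are new, and it does not protect the rates within an arm.
- **Interval history and the relatedness rule.** A history taken a week after the first dose can ask when a symptom began, and the named outcome is FMT-related events, not all events. A symptom known to predate dosing should fail the relatedness test. This stands in part: the filter exists, but what it works from is recall after dosing.
- **Exclusions.** They are broad, and applying them means asking about bowel and gastrointestinal history before dosing. That reduces the number of prior symptoms without recording those that remain.
- **The form itself.** The Side Effect Assessment document was not supplied. If it asks about onset or change from usual, the gap is smaller than the schedule suggests.
- **The assumed prevalence.** Nothing in the documents supports 10% to 40%. At 5%, the chance of a gap of 3 or more is about 2%.

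A reader might infer that prior symptoms cannot be separated from new ones at all, or that the placebo comparison of side effects is biased. The documents support neither, for the reasons in the first two items. A reader might also expect a week-0 form to separate clamp and fasting effects from capsule effects. It would not: if completed before the clamp, it leaves the clamp, the fast and the capsules all in the same interval. The placebo arm does that job, because both arms have the same procedures.

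**Conclusion.** The point holds as a gap in data collection. No symptom assessment is scheduled before the first capsules, so the trial has no scheduled per-participant baseline for an outcome tied to one of its stated purposes. The consequence is possible misclassification of mild prior symptoms as new events, possible inflation of event rates within each arm, and a chance imbalance of 3 or more people in prior symptoms with probability about 8% to 30%.

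That range rests on an assumed prevalence of 10% to 40% and on 12 participants per arm, and it reaches the safety results only to the extent that prior symptoms are reported and counted as new. Whether the unsupplied form already asks about onset is unknown. The gap does not invalidate the trial and has no bearing on sample size, alpha or power. It is worth closing because it is cheap to close and because a pre-dose record cannot be obtained once the first capsule has been taken.

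**What to change.** Add the existing Side Effect Assessment to the Week 0 list in section V, completed before the first capsule and preferably before the clamp. In section VI, state that symptoms new or worse in grade than at week 0 will be reported by arm, alongside the FMT-related adverse events already named in Aim 2. If the form already asks about onset, keep that question.

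The cost is a few minutes on a visit day already planned at 5 hours, one line in the schedule and one sentence in the analysis section. No new visit, form or staff is needed.

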#### Week 12 (1 hour)

- Interval side effect assessment (see Side Effect Assessment document)
- Height, weight measurements
- Fasting blood samples for measurements of HOMA-IR, lipids, CRP and HbA1c.
- 48-hour food recall
- Women of child bearing potential will have a urine pregnancy test
- Whole body DXA scan for body composition analysis
- Fecal Collection

#### Week 24 (Month 6) Follow Up (5-20 minutes)

- If not enrolled in the extension study, interval side effect and self-reported weight assessment will occur by phone (see Phone Follow-Up document)
- If enrolled in the optional extension substudy, subjects will come for an in-person visit to MGH.
- Fecal collection
- Fasting blood samples for measurements of HOMA-IR, lipids, CRP and HbA1c.
- Interval side effect assessment will be conducted.
- Note that we will allow a  $\pm 2$  month window for scheduling this visit

#### Month 12 (1 hour; optional extension study)

- Interval side effect assessment (see Side Effect Assessment document)
- Height, weight measurements
- Fasting blood samples for measurements of HOMA-IR, lipids, CRP and HbA1c.
- 48-hour food recall
- Women of child bearing potential will have a urine pregnancy test
- Whole body DXA scan for body composition analysis and DXA scan of lumbar spine and proximal femur to assess bone mineral density
- Fecal Collection
- Note that we will allow a  $\pm 2$  month window for scheduling this visit

### **C. Technical Methods**

Phone screen: Phone discussion to explain approach and alternatives briefly (10-20 minutes). The purpose of this discussion is to ensure subjects who cannot get past the aesthetic concerns of this procedure do not spend time coming to the hospital for an in

person discussion. People may wish time to consider after having this discussion. Those who wish to have an in person discussion, even if not decided upon having the procedure are welcome to come in for further discussion. The consent form is provided at this time, if desired.

FMT and placebo capsule preparation: We will generate FMT capsules from donors per our FDA-approved operating procedures. Donors will be asked to refrain from eating common allergens within 5 days of the donation (tree nuts, eggs, peanuts, shellfish) but otherwise not alter their diets. Volunteers will have an interim health query for febrile, system, and GI symptoms at the time of donation, and defer collection if there is any change in health status. Processing is carried out under aerobic conditions. A fecal suspension is generated in normal saline without preservatives. Materials are sequentially sieved to remove particulate material. The final slurry is concentrated by centrifugation and re-suspended in saline at 1/10 volume of the initial sample with 10% glycerol added as a bacterial cryoprotectant. Fecal matter solution is pipetted in size 0 capsules (650 $\mu$ L), which are closed and then secondarily sealed in size 00 capsules. Capsules are stored frozen at -80 $^{\circ}$ C for up to 6 months at which point they are discarded if not used. 1-2 hours prior to administration they will be transferred to -20 $^{\circ}$ C and then transported to the dosing site on dry ice. Commercially available acid-resistant hypromellose capsules (DRCaps, Capsugel, Cambridge, MA, USA) are used. Each inoculum is prepared from the feces of a single donor. This project is under FDA IND #16643.

FMT CAPSULES

PLACEBO CAPSULES

Placebo capsules will consist of a combination of powdered cocoa and gelatin in normal saline/glycerol (same vehicle as FMT capsules). Gelatin is added to make the placebo solution more viscous and physically fill capsules in the same way that the standard FMT inoculum does for appearance purposes. Placebo capsules are identical in appearance to FMT capsules, and are included in the above mentioned FDA IND # 16643.

FMT and placebo capsule administration: Subjects will be NPO at least 4 h prior to and for 1 hour following capsule intake on each day, to minimize risk of vomiting during ingestion of capsules. Subjects will be handed each capsule by an investigator and asked to take each capsule with a sip of water. Subjects will be asked to drink at least 12 oz of water during administration to facilitate dilution of stomach contents and transit into the small intestine. In the event of vomiting subjects will be observed, and not re-dosed.

Subjects are evaluated after taking capsules by the study investigators, typically for 15 minutes. Immediate side effects are very uncommon in our experience. Capsules are odorless and tasteless and do not dissolve in the acidic environment of the stomach. (In our study of capsules to date we have had 1/61 subjects who complained of nausea during administration, and this individual had concurrent psychiatric illness and concurrent irritable bowel syndrome diagnosed by an outside gastroenterologist. One child vomited 4 hours after capsules were administered.).

Subjects receive a copy of the signed consent form to take home and an information sheet (attached) on symptoms to monitor and study physician phone numbers. All patients have our contact numbers and will be encouraged to call for any concerns. Subjects are asked to inform us if they require the initiation of antibiotics for intercurrent clinical illness, during the study period.

Subjects will receive capsules at weekly intervals ( $\pm$  2 days) for weeks 0-5.

Subject counseling: Subjects will be counseled to remain on the same diet that they are currently on and not to initiate any major exercise regimens throughout the primary 12 week study period. In addition, women with child-bearing potential will be informed that they need to use contraception throughout the study. If they are taking a hormonal contraceptive, they need to remain on such until the end of the study. If they are not using a hormonal contraceptive, they will need to use other forms of birth control, such as barrier methods with a spermicide, IUD, or abstinence. We will ask that they not actively initiate or discontinue hormonal treatments during the study, as this may confound our assessments of body weight and insulin sensitivity.

Height, weight measurements: Height and weight measurements will be performed in triplicate in light clothing without shoes. Waist circumference will be measured as the narrowest circumference between the lower costal margin and iliac crest in the standing position at the end of a normal exhalation. All measurements will be performed using standardized protocols by bionutritionists at the MGH Clinical Research Center.

Fecal sampling: Fecal samples will be collected from recipients at weeks 0, 1, 3, 5, 6, and 12 (and 6 and 12 months if subjects choose to participate in the optional extension study), and stored in a  $-80^{\circ}\text{C}$  freezer according to established protocols. Recipients will be given instructions and stool collection kits to bring home (see Stool Collection document). All samples will be brought to MGH by the patient.

DXA: Whole body, hip and spine DXA scans will be performed. DXA scans of the whole body will be obtained at baseline, 6 and 12 weeks (and 12 months if subjects choose to participate in the optional extension study). For those participating in the optional bone density substudy, DXA scans on the spine and hip will be obtained at baseline and 12 months. Measurements will be performed on QDR Hologic Discovery A machines. Body composition (lean body, fat mass including subcutaneous and visceral compartments) and bone density (PA spine, total hip, and femoral neck) will be measured using standard DXA analysis procedures as recommended by the manufacturer. The effective absorbed

radiation dose for each full body DXA scan is 0.0084 mSv and for the hip and spine DXA scans is 0.022 mSv. The total amount of radiation from participation in this study and the optional extension study is 0.076 mSv for these procedures.

Hyperinsulinemic-euglycemic clamp: Subjects will undergo clamp studies to assess peripheral insulin sensitivity at week 0 and week 6. This procedure is performed at the MGH CRC. Peripheral insulin sensitivity will be determined during the last 20 minutes of the clamp using the DeFronzo method. Clamp procedure will be as follows.

- Subjects will be asked for fast for 12 hours prior to their study visit.
- Insulin infusate will be prepared by the MGH pharmacy.
- Two intravenous (IV) catheters will be inserted: (1) one placed in the hand when access is available, otherwise in the forearm or antecubital space, to be used for venous sampling; (2) one placed in the antecubital space or proximal forearm and used for administration of insulin and 20% dextrose as below.
- The hand/forearm with the IV that will be used for venous sampling will be placed in a warming box for the duration of the clamp procedure, although it may be withdrawn if the subject finds the warmth uncomfortable.
- At time “0” (approximately 9am), a priming dose of 300 mU/m^2/min of insulin will be given for 2 minutes followed by a continuous infusion of 60 mU/m^2/min for the next 118 minutes.
- From 0-120 minutes, a sample ( $\leq 0.5$ cc) of venous blood will be drawn every 5 minutes for assessment of glucose using a Hemocue glucose analyzer. Each sample is run twice in the Hemocue analyzer, with an additional third run if the difference between the first two runs is  $\geq 4$ mg/dL. Samples for serum insulin concentration will be drawn at times 0, 80, 100, 120 minutes.
- Starting at 5 minutes, a variable 20% dextrose infusion will be administered to achieve a target glucose of 90mg/dL (range 85-95mg/dL). The rate will be adjusted by the investigator, an MD or NP who is trained in clamp procedure. The initial infusion rate of 20% dextrose will be 0-30cc/hr, with the exact rate determined by the investigator based on the subject’s fasting glucose, available clinical information, and, if available, data from the subject’s previous clamp procedure for the study. (For example, a subject who is known clinically to be insulin resistant and has a fasting glucose of 110mg/dL would be started at a rate of 0cc/hr, whereas a lean, muscular subject who exercises regularly and has a fasting glucose of 70mg/dL would be started at 30cc/hr.)
- The rate of 20% dextrose infusion will be adjusted up or down for the duration of the clamp procedure by the investigator. Rate changes of 0-40cc/hr will be made by the investigator every 5 minutes, based on the subject’s venous glucose and rate of change in glucose, to achieve target glucose of 90mg/dL.
- At 120 minutes, the insulin infusion will be discontinued, and the glucose infusion will continue for 30 more minutes. During this time, subjects will be given a meal. At 150 minutes, venous glucose will be checked, and the glucose infusion will be discontinued if venous glucose  $\geq 80$ mg/dL. If glucose is  $< 80$ mg/dL, the glucose infusion will be continued and will be weaned by the investigator at the bedside, with repeat venous glucose sampling every 10 minutes until the glucose is  $\geq 80$ mg/dL and the infusion is stopped.

- After the clamp, all subjects are counseled concerning the symptoms of hypoglycemia and are asked to report immediately any symptoms. Subjects are observed on the CRC for at least 20 minutes following discontinuation of glucose infusion.

This procedure assumes that the hyperinsulinemic state is sufficient to completely suppress hepatic glucose production and that there is no net change in blood glucose concentrations under steady-state conditions. Under such conditions, the rate of glucose infused is equal to the rate of whole-body glucose disposal (GDR) or metabolizable glucose (M) and reflects the amount of exogenous glucose necessary to fully compensate for the hyperinsulinemia.

Indirect Calorimetry: A ventilated hood calorimeter (VMAX Encore; Carefusion Corp, Yorba Linda, CA) will be utilized to assess resting energy expenditure (REE) and respiratory quotient (RQ) by determining oxygen consumption (VO2) and carbon dioxide production (VCO2) for 20 minutes under fasting conditions before the clamp. REE will be normalized to lean body mass as determined by dual-energy x-ray absorptiometry.

Compensation: Recipients will be compensated \$750 for completion of the study. \$100 for completing the baseline visit, \$400 for completing the week 6 visit (\$100 for the clamp visit, \$50 per capsule administration visit), and \$250 for the week 12 visit. If subjects choose to participate in the optional extension study, they will be compensated an additional \$100 (\$25 for 6 month visit and \$75 for 12 month, visit). They will also receive either a parking voucher or up to \$20 to cover travel expenses at each visit

